- Subjects who experience stable disease (SD) at the initial response assessment at 8 weeks from initiation of primary nivolumab therapy, with the subsequent scan in 8 weeks (± 7 days) documenting CR/PR which is maintained at the next imaging assessment in 8 weeks (± 7 days) (i.e., ~24 weeks from initiation of nivolumab).

Patients who have SD on initial assessment followed by CR/PR on first confirmatory assessment which does not persist on the second confirmatory imaging assessment will be allocated to Arm B as CR/PR was not persistent and confirmed on consecutive imaging assessments.

Subjects with confirmed PR/CR (arm A) will discontinue nivolumab and be followed with serial imaging assessments every 8 weeks. If progressive disease (PD) develops, therapy with nivolumab will be resumed and will not be discontinued if a subsequent PR or CR were to occur. Subjects who experience subsequent PD following re-initiation of nivolumab, will be treated with nivolumab + ipilimumab every 3 weeks x 2 doses and will continue nivolumab. All patients will continue on treatment with nivolumab alone every 4 weeks which will begin 5 weeks \pm 3 days after the last dose of nivolumab + ipilimumab. For subjects who experience a PD on nivolumab and ipilimumab, treatment will be discontinued.

If by 24 weeks, subjects have not demonstrated a persistent CR/PR confirmed on at least two serial scan assessments, then subjects will be allocated to Arm B at the 24 week time point.

Arm B (persistent PD/SD) includes the following patient scenarios:

- Subjects who experience PD at 8 weeks (initial response assessment) on primary nivolumab therapy which is then confirmed by a second scan within 4 weeks (\pm 7 days). The confirmatory scan is not required if the site investigator determines that this is clinically detrimental;
- Subjects who initially experience SD at 8 weeks (initial response assessment), which is confirmed with a second scan showing SD in 8 weeks (\pm 7 days)
- Subjects who have received at least 3 doses of nivolumab and may have signs and/or symptoms concerning for early clinical progression with radiographic evidence of PD before 8 weeks
- Subjects who do not meet the criteria for allocation into Arm A given lack of persistent CR/PR confirmation on serial and consecutive imaging within the first 6 months of the study will be allocated to Arm B by the 6-month time point.

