6. TREATMENT PLAN

After informed consent has been obtained in writing, the subject will then undergo screening procedures and will enter the trial after successful screening. The subject must be willing to undergo a MANDATORY fresh tumor biopsy prior to treatment following successful screening and registration unless the site investigator deems the procedure medically unsafe.

Subjects who have signs and/or symptoms concerning for early clinical progression can undergo imaging before the initial 8 week imaging time point. In this scenario, if there is evidence of radiographic progression as per RECIST version 1.1, subjects will be allocated immediately to Arm B as long as they have received at least 2 doses of nivolumab (two doses of 480mg IV q 4 wks). Subjects who received fewer than 2 doses of nivolumab (480mg dosing) with early progression can either discontinue from study or may continue on to receive at least 2 doses of nivolumab before reassessing response at treating investigator's discretion. The per protocol 8 week scans should still be done on schedule even if earlier scans are done and compared to baseline for initial response assessment which should then be confirmed at the 16 week time point per protocol.

Primary Treatment with Nivolumab

Eligible subjects will be enrolled and will receive primary treatment with nivolumab 480 mg IV (D1) for 2 cycles. Each Cycle = 28 days. After 2 cycles (8 weeks +/- 7 days), all subjects will have initial disease assessment scans.

Arm A: CR or PR Response after Primary Treatment with Nivolumab:

- For subjects allocated to Arm A, nivolumab will be discontinued and subjects will be followed with serial imaging assessments every 8 weeks (Observation).
- If PD develops, therapy with nivolumab 480 mg IV every 4 weeks will be resumed. At this time, subjects will be asked to undergo an optional fresh tumor biopsy. Subjects will have disease assessment scans every 8 weeks (+/- 7 days). Nivolumab will continue until PD is documented.

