- Subjects who experience subsequent PD following re-initiation of nivolumab will have ipilimumab 1 mg/kg IV every 3 weeks x 2 doses added. During this time, nivolumab 3 mg/kg IV will be administered every 3 weeks to coincide with ipilimumab 1 mg/kg x 2 doses. Treatment with nivolumab alone 480 mg IV every 4 weeks will begin 5 weeks ± 3 days after the last dose of nivolumab + ipilimumab. **NOTE:** When ipilimumab is added, the first radiology imaging from the time that combination therapy with nivolumab and ipilimumab is initiated will be obtained after 3 cycles (12 weeks ± 7 days) instead of 2 cycles (8 weeks). Subsequent imaging assessments after this first imaging assessment will occur every 2 cycles (8 weeks +/- 7 days).
- Subjects with CR/PR/SD after nivolumab plus ipilimumab will continue nivolumab alone starting 5 weeks +/- 3 days after the last dose of combination therapy with nivolumab and ipilimumab. When given alone, nivolumab will be given at 480 mg IV

every 4 weeks. If disease assessment scans after 3 cycles (12 weeks) from the time of initiation of combination therapy with nivolumab and ipilimumab show CR/PR/SD, subjects will continue nivolumab alone until PD is documented. Subsequent imaging assessments after this first imaging assessment will occur every 2 cycles (8 weeks \pm 7 days).

- For subjects who experience a PD on nivolumab and ipilimumab, treatment will be discontinued.

Arm B: SD/PD Response after Primary Treatment Nivolumab:

- For subjects allocated to Arm B, ipilimumab 1 mg/kg IV every 3 weeks x 2 doses will be added. During this time, nivolumab 3 mg/kg IV will be administered every 3 weeks to coincide with ipilimumab dosing x 2 doses and then nivolumab will be continued at 480 mg IV every 4 weeks thereafter. Treatment with nivolumab alone every 4 weeks will begin 5 weeks \pm 3 days after the last dose of nivolumab + ipilimumab at the start of Cycle 3/Day 1 following primary treatment with nivolumab. Subjects will be followed with serial imaging assessments every 8 week (+/- 7 days) and will continue nivolumab. If PD develops, treatment will be discontinued.

NOTE: When ipilimumab is added, the first radiology imaging from the time that combination therapy with nivolumab and ipilimumab is initiated will be obtained after 3 cycles (12 weeks \pm 7 days) instead of 2 cycles (8 weeks +/- 7 days). Subsequent imaging assessments after this first imaging assessment will occur every 2 cycles (8 weeks +/- 7 days).

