- 4: TSH and free T4 will be done at screening and every 2 cycles (8 weeks ± 7 days).
- 5: For women of childbearing potential (WOCBP): urine or serum βhCG. If a urine test is done and it is positive or cannot be confirmed as negative, a serum pregnancy test will be required. WOCBP should be counseled regarding the importance of contraception from the time of screening until 180 days after last dose of study drug(s). If a subject communicates that pregnancy is possible, a serum βhCG should be performed per site investigator's discretion.
- 6: Hepatitis B virus (HBV) serology (HBsAg, antibodies against HBsAg, antibodies against hepatitis B core antigen), and HCV serology (anti-HCV) will be performed. HBV DNA test is required for subjects who have known positive serology for anti HBc. HCV RNA test is required for subjects who have known positive serology for anti HCV.
- 7: Radiology Imaging at screening to include: Diagnostic CT chest and CT or MRI of the abdomen and pelvis and MRI of the brain. If a subject is not able to obtain an MRI, CT imaging with contrast is acceptable. If a subject is not able to receive contrast, CT head without contrast is acceptable. Radiology Imaging during Primary Treatment: Initial scans will be done after 2 cycles (8 weeks +/- 7 days) of nivolumab. Subjects with PR/CR/SD will have confirmatory scans 8 weeks later (+/- 7 days). Confirmatory scans for subjects with PD are not mandatory but may be attained 4 weeks later if clinically feasible (+/- 7 days). Subjects who have two serial consecutive imaging assessments (8 weeks +/- 7 days apart) which demonstrate CR/PR within the first 6 months of study will be allocated to Arm A. All other subjects who do not meet this criteria will enter Arm B by the 6 month time point. Subjects have who signs and/or symptoms concerning for early clinical progression can undergo imaging before 8 weeks (+/- 7 days). In this scenario, if there is evidence of radiographic progression, subjects may be allocated to Arm B immediately, assuming they have received at least 3 doses of nivolumab. For Single Cell Sequencing Cohort MRI or CT of the Brain will not be collected at screening.
- 8: Primary Treatment: Nivolumab will be administered on Day 1 (+/- 3 days) of each 28-day cycle for 2 cycles. After 2 cycles, disease assessment will occur. Nivolumab alone will continue until disease status documented with confirmatory scans (See Footnote 7) or site investigator

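### Early-progressor route to Arm B: Section 2.7 and calendar footnote 7 require at least 3 nivolumab doses, Section 6 at least 2, and 4-weekly dosing leaves almost no room for a third dose before week 8

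*Combined protocol and SAP*

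**What the plan says.** Three places in the current text govern the same decision.

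- **Section 2.7, Arm B scenarios.** The early route is for "Subjects who have received at least 3 doses of nivolumab and may have signs and/or symptoms concerning for early clinical progression", with progression shown on imaging before 8 weeks.
- **Section 8, primary-treatment calendar, footnote 7.** On early radiographic progression, "subjects may be allocated to Arm B immediately, assuming they have received at least 3 doses of nivolumab".
- **Section 6.** Early progressors go to Arm B at once "as long as they have received at least 2 doses of nivolumab (two doses of 480mg IV q 4 wks"). A separate rule covers those below that count: "Subjects who received fewer than 2 doses of nivolumab (480mg dosing) with early progression can either discontinue from study or may continue" until they have had 2 doses and are then reassessed, at the treating investigator's discretion.

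The schedule around this decision is:

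- Footnote 8 of the same calendar: "Nivolumab will be administered on Day 1 (+/- 3 days) of each 28-day cycle for 2 cycles".
- Section 6: "After 2 cycles (8 weeks +/- 7 days), all subjects will have initial disease assessment scans".
- On the ordinary route in Section 2.7, progression at the week-8 scan is confirmed by a second scan about 4 weeks later (±7 days), unless the investigator judges that step detrimental. Footnote 7 makes the second scan optional.
- Footnote 7 also has a catch-all: "All other subjects who do not meet this criteria will enter Arm B by the 6 month time point".
- Arm B treatment, Section 6: "For subjects allocated to Arm B, ipilimumab 1 mg/kg IV every 3 weeks x 2 doses will be added".

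**The concern.** The route exists for a subject who is clinically worsening and has imaging proof of progression before the routine scan. With exactly 2 doses given, that subject qualifies under Section 6 but not under Section 2.7 or footnote 7. No rule states which text takes precedence, and sites work from both the treatment plan and the calendar.

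The number 3 also looks wrong in itself. Only 2 doses are planned before the first scan, so a 3-dose minimum comes close to closing the route that the sentence opens.

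What is at stake is when a progressing subject may move to the arm that adds ipilimumab, and whether sites apply the same rule. Whichever text a site follows, it departs from another part of the protocol, and Appendix D (Section 3.8) requires departures to be reported.

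**Working it through.** **Inputs.** Day 1 is the first dose. Doses are 28 days apart, ±3 days (Section 6.1 and calendar footnote 8). The first scan is at 8 weeks ±7 days (Section 6). The minimum dose count is 3 (Section 2.7, footnote 7) or 2 (Section 6).

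**Dose and scan days.**

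- Dose 2: 1 + 28 = day 29.
- Dose 3, nominal: 1 + 28 + 28 = day 57.
- Dose 3, earliest with the window counted from the first dose: 57 − 3 = day 54.
- Dose 3, earliest with both intervals shortened: 1 + 25 + 25 = day 51.
- Week-8 scan: 1 + 56 = day 57, with a window from 57 − 7 = day 50 to 57 + 7 = day 64.

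**Does the stated 3 fit?** On the nominal schedule, 2 doses (days 1 and 29) have been given before day 57. A third before week 8 requires use of the −3-day allowance. A third before day 50 is not possible under any reading, since the earliest is day 51.

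**Days on which the dose count is met.** Section 2.7 sets the limit at 8 weeks, but a scan from day 50 onward already counts as the scheduled one, so both cut-offs are shown.

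| Minimum doses | Before the scan window opens (last day 49) | Before nominal week 8 (last day 56) |
|---|---|---|
| 3, nominal schedule | 0 | 0 |
| 3, dose 3 on day 54 | 0 | 56 − 54 + 1 = 3 |
| 3, dose 3 on day 51 | 0 | 56 − 51 + 1 = 6 |
| 2, dose 2 on day 29 | 49 − 29 + 1 = 21 | 56 − 29 + 1 = 28 |

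**Wait until the first scheduled scan under the 3-dose text.**

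- Progression on day 29: 57 − 29 = 28 days (50 − 29 = 21 to 64 − 29 = 35 over the scan window).
- Progression on day 43: 57 − 43 = 14 days (50 − 43 = 7 to 64 − 43 = 21).

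These figures run to the scan, not necessarily to allocation. If a confirmatory scan is then done, allocation can come up to about 28 days (±7) later still: 28 + 28 = 56 days after progression on day 29, and 14 + 28 = 42 days after progression on day 43. If confirmation is waived, nothing is added.

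**Ipilimumab start.** Section 6 gives no interval between the last 480 mg dose and the first combination dose, so a delay in dosing cannot be calculated. As an illustration only, suppose the combination must wait for the next 28-day cycle. A subject dosed on day 29 would then start on day 57 under either rule, provided confirmation is waived. If the combination may start at once, the wait carries over into dosing.

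**The case against.** **The zero depends on the cut-off.** Section 2.7 says before 8 weeks, not before the scan window opens. Against that limit, up to 3 or 6 days exist. This stands. A reader might infer that a third dose before week 8 is impossible, but the −3-day allowance permits one. The days gained already lie inside the routine scan window, so they add little as an early route.

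**Section 6 is already workable.** It spells out the two 480 mg doses and covers the subject who has had fewer. A site reading only Section 6 has complete instructions. That shows which number makes sense, but it does not remove the other two statements.

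**No treatment consequence is shown.** This also stands. The start of ipilimumab under each rule cannot be worked out, and neither can the number of subjects concerned. A reader might infer that the conflict deprives subjects of ipilimumab or biases the Arm B response rate. The documents do not support that: those who miss the early route can still enter through the week-8 scan or the 6-month catch-all.

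**The catch-all makes the point moot.** This goes too far. Section 6.5 lets subjects come off therapy for intercurrent illness, adverse events or withdrawal. Section 6 also lets some stay on nivolumab alone. Eventual Arm B treatment is likely for many but not guaranteed.

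**Conclusion.** The plan is wrong as written: an allocation rule is stated in two incompatible ways, and one version nearly blocks the route it creates. Under the 3-dose text the early route is usable on 0 days before day 50 and on 0 to 6 days before nominal week 8. With dose 2 on day 29, the Section 6 text gives 21 and 28 days. A site following the 3-dose text would hold a symptomatic subject with radiographic progression at least until the scheduled scan, about 28 days after progression on day 29 or 14 days after progression on day 43, and up to about 4 weeks (±7 days) longer if a confirmatory scan is done.

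The day counts assume dosing within the permitted windows and no dose delays; a delay would only push dose 3 later. The waits assume the week-8 scan is done on its nominal day.

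The conclusion concerns consistent conduct, not the statistics. A reader might take a fault in arm allocation to undermine the Arm B two-stage design. It does not: the sample size, power and type I error in Section 13.3 rest on response rates and subject numbers, and the dose count does not enter them.

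**What to change.** In Section 2.7 (Arm B scenarios) and in footnote 7 of the primary-treatment calendar, change the minimum from 3 nivolumab doses to 2, to match Section 6. Raising Section 6 to 3 would not work: it would leave the route nearly unusable and would not fit that section's rule for fewer than 2 doses.

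The cost is one number in two places. No subjects, scans or procedures are added, and the analysis does not change.

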3. STUDY OBJECTIVES

3.1 Objectives

3.1.1 Primary Objectives

- Assess the proportion of subjects with persistent complete response (CR) or partial response (PR) at one year after

nivolumab discontinuation (Arm A)

- Assess the proportion of subjects with progressive disease (PD)/stable disease (SD) that convert to PR/CR at one year upon the addition of ipilimumab to nivolumab (Arm B)

3.1.2 Secondary Objectives

- Assess progression-free survival (PFS) and overall survival (OS) rates in Arm A and Arm B
- To assess the rate of re-initiation of nivolumab (salvage) therapy (arm A)
- Assess the immune-related ORR (irORR) in subjects in Arm A and B
- Assess safety and toxicity in study arms A and B
- Summarize PR/CR rate, PFS, and OS in the overall cohort and by each arm according to subgroups:
 - International mRCC Database Consortium (IMDC) risk groups.
 - Untreated versus previously treated subjects
 - Histologic subtype (clear cell versus non-clear cell renal cell carcinoma (RCC) subtypes; sarcomatoid components present versus absent)

3.1.3 Correlative/Exploratory Objectives

- Evaluate the relationship between tumor-infiltrating lymphocytes (TILs), programmed death-ligand 1 (PD-L1) tumor expression, and other tissue biomarkers with efficacy outcomes (proportion of PR/CR, PFS, OS)
- Evaluate the relationship between PD-L1 status in archival tissue and in fresh tumor specimens
- Evaluate mechanisms of response to nivolumab in fresh tumor specimens obtained at baseline in subjects with a durable response to treatment (≥ 1 year)
- Evaluate mechanisms of intrinsic and acquired resistance to nivolumab and ipilimumab treatments in fresh tumor specimens obtained at time of radiographic progression
- Assess molecular mechanisms of resistance to treatment via circulating free DNA (cfDNA) assessment and to correlate cfDNA molecular profile with metastasis biopsy molecular profile
- Assess molecular mechanisms of resistance to treatment via circulating tumor cell (CTC) assessment
- Correlate CTC molecular profile with metastasis biopsy molecular profile

- Assess mechanisms of response and resistance to treatment via single cell molecular assessment (transcriptome assessment)
- Correlate single cell molecular profile with metastasis biopsy molecular profile

4 ELIGIBILITY CRITERIA

4.1 Inclusion Criteria

Subject must meet all of the following applicable inclusion criteria to participate in this study:

1. Age \geq 18 years at the time of consent.
2. ECOG Performance Status of \leq 2 within 28 days prior to registration.
3. Unresectable advanced or metastatic RCC to include both clear cell and non-clear histologies.

Patients who have suspected metastatic RCC, which has not yet been pathologically proven, may be enrolled if they plan to undergo a cytoreductive nephrectomy, metastectomy, or biopsy. Fresh tissue from one of these procedures can be used for the clinical trial requirements (eligibility #) as well as serve as pathologic confirmation of RCC. The pathologic confirmation must be documented prior to C1D1.

Single Cell Sequencing Cohort only: Histology must have predominant clear cell component.

4. Availability at the study site of formalin-fixed, paraffin-embedded (FFPE) archival tumor specimens, when available, and willingness of the subject to undergo mandatory fresh tumor biopsy prior to treatment initiation. If a target lesion is biopsied at screening, this lesion must be followed as non-target lesion after the biopsy unless it is the patient's only target lesion. If there is only one target lesion, it should be followed as a target lesion regardless.
 - a. The archival specimen must contain adequate viable tumor tissue.
 - b. The specimen may consist of a tissue block (preferred and should contain the highest grade of tumor) or at least 30 unstained serial sections. Fine-needle aspiration/ biopsy, brushings, cell pellet from pleural effusion, bone lesion, bone marrow aspirate/biopsy are not acceptable.

Previously untreated or treated subjects with no limit on prior lines of systemic therapies are allowed. Patient may have received prior adjuvant therapy.

Single Cell Sequencing Cohort only: Can either have had no prior systemic therapy (treatment naïve) for RCC, prior IFN- α or IL-2, or a maximum of 1 prior VEGF targeted therapy (VEGFR TKI-based regimen or bevacizumab) for RCC. Agents given in combination in the first line would count as 1 regimen (e.g., Lenvatinib +

Everolimus).

5. Measurable disease as defined by Response Evaluation Criteria In Solid Tumors RECIST 1.1 within 28 days prior to registration.
6. Demonstrate adequate organ function as defined in the table below. All screening labs to be obtained within 28 days prior to first study treatment.

System	Laboratory Value
Hematological	
White blood cell (WBC)	≥ 2500 cells/ μ L
Absolute Neutrophil Count (ANC)	≥ 1500 cells/ μ L
Platelet count (plt)	≥ 100,000/ μ L
Hemoglobin (Hgb)	≥ 9 g/dL (transfusions allowed)
Absolute lymphocyte count	≥ 500 cells/ μ L
Renal	
Serum creatinine OR Calculated creatinine clearance ¹	≤ 1.5 x ULN ≥ 40 mL/min
Hepatic and Other	
Bilirubin ³	≤ 1.5 × upper limit of normal (ULN)
Aspartate aminotransferase (AST) ²	≤ 2.5 × ULN
Alanine aminotransferase (ALT) ²	≤ 2.5 × ULN
Alkaline Phosphatase ²	≤ 2.5 × ULN
Albumin	> 2.5 g/dL
Coagulation	
International Normalized Ratio (INR) or Prothrombin Time (PT) Activated Partial Thromboplastin Time (aPTT)	≤ 1.5 × ULN (unless on prophylactic or therapeutic dosing with low molecular weight heparin, or oral anticoagulants (eg. coumadin, rivaroxaban))

¹ Cockcroft-Gault formula will be used to calculate creatinine clearance (See SPM)

² Subjects with documented liver metastases should have AST and ALT ≤ 5 x ULN. Subjects with documented liver or bone metastases should have alkaline phosphatase ≤ 5 x ULN

³ Subjects with known Gilbert's disease should have a serum bilirubin ≤ 3 x ULN.

7. Females of childbearing potential must have a negative serum pregnancy test within 28 days prior to registration. **NOTE:** Females are considered of child bearing potential unless they are surgically sterile (have undergone a hysterectomy, bilateral tubal ligation, or bilateral oophorectomy) or they are naturally postmenopausal for at least 12 consecutive months.
8. Females of childbearing potential and males must be willing to abstain from heterosexual activity or to use 2 forms of effective methods of contraception from the time of informed consent until 150 days after treatment discontinuation for females and 210 days after treatment discontinuation for males. The two contraception methods can be comprised of two barrier methods, or a barrier method plus a hormonal method.
9. As determined by the enrolling physician or protocol designee, ability of the subject to understand and comply with study procedures for the entire length of the study.

